## **6. Data and Safety Monitoring Responsibilities:**

Data and safety monitoring will be the primary responsibility of all persons with patient contact, the research nurse and other staff, [name] and [name]. In addition, [name] will review the serum calcium safety labs for any evidence of hypercalcemia and will review all AEs and SAEs. [name] in cooperation with the research nurse and site investigator will be responsible for reporting these events to the internal safety officer and to KAI who will distribute to the DSMB safety officer and NIAMS. They will also be sure that each IRB and the FDA are notified.

For any unanticipated problems or serious adverse events, including hospitalizations, cancers or deaths, the internal safety officer and KAI who will distribute to the DSMB safety officer and NIAMS within 48 hours of learning of the complication. The IRB and FDA (IND 126129; [name]) will be notified of unanticipated problems and SAEs as per their guidelines.

Teriparatide: We will initially minimize risks of teriparatide treatment by excluding subjects who might be at higher risk for adverse events. The risks of subcutaneously administered teriparatide injections include local skin irritation, dizziness, leg cramps, nausea, arthralgias, myalgias, hypercalcemia and hypercalciuria.

Although no increase in risk of renal stones has been seen in clinical trials with teriparatide, potential subjects with recent kidney stones (within 2 years) or a history of multiple stones will be excluded from the protocol to minimize this risk. Because teriparatide treatment has a boxed warning regarding risk of osteosarcoma, potential subjects who have an increased risk of osteosarcoma, such as those with Paget's disease, prior history of bone tumor, or history radiation therapy will be excluded from participation in the trial. Also, to minimize risk of hypercalcemia or hypercalciuria, potential volunteers with evidence of hyperparathyroidism will be excluded from participating in the trial. To monitor any occurrence of adverse events, side effects, or difficulty with medication administration with TPTD, subjects will be called weekly by the Research Nurse during TPTD treatment. In cases where side effects are significant and interfering with quality of life (e.g. musculoskeletal pain or nausea), volunteers will be told to reduce TPTD administration to every other day until the symptoms abate.

**Monitoring of Hypercalcemia:** The major safety evaluation of this study is a check for hypercalcemia which will first be assessed at 4 weeks after starting TPTD when calcium levels are found to peak. The development of hypercalcemia may be dependent on an individual's baseline serum calcium level and calcium supplement exposure. Therefore, volunteers will be counseled by the Research Nurse about optimizing dietary calcium intake, and avoiding calcium supplement use in order to prevent the development of hypercalcemia. Calcium supplements will be used only as needed to bring daily calcium intake to 1000 mg a day. Serum calcium levels will be checked at every visit, which occur monthly for the first 3 months after TPTD or placebo initiation and then, during the open label with teriparatide treatment, levels will be checked every three months. Subjects will be advised not to take the TPTD or placebo prior to the blood sample being collected (levels will be obtained at least 16 hours after the last TPTD dose). Serum samples will be analyzed within 24 hours of sample procurement and will be reviewed by the Safety Officer [name] within 24 hours of receipt of result.

If the serum calcium is above 11.5 mg/dl, calcium supplements or dietary calcium will be reduced and the level will be checked again within 3 days. If the level remains >11.5 mg/dl; TPTD will be given on alternate days.

If the serum calcium is between 10.5 and 11.5 mg/dl, calcium supplements or dietary calcium will be reduced and the level will be checked again within 10 days. If serum calcium levels are persistently above 10.5 mg/dl, volunteers will be advised to take TPTD every other day.

In multiple prior trials involving TPTD treatment in hundreds of patients, we have never been required to reduce the dose of TPTD due to hypercalcemia.

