**Baseline Visit:** Baseline visits will be scheduled when all results are in and within one month of fracture. Subjects will be seen in the morning after an overnight fast. Blood will be drawn and subjects will be allowed breakfast. Vitamin D supplements (1000 IU daily) will be provided to help to maintain adequate 25OHD serum levels and calcium intake will be reviewed. A blood sample will be collected at baseline and at every visit to assess calcium level for safety. Blood samples for biochemical indices of bone turnover (serum PINP for bone formation and serum CTX for bone resorption) and 25(OH)D will be obtained at baseline and every month and analyzed by batch at the Helen Hayes Hospital Regional Bone Center. Subjects will complete the lower extremity physical function tests, an Activities of Daily Living (ADLs) and SF-36 physical function survey, NRS for pain and a survey with pill count to determine narcotic use. Subjects will be randomly assigned (with separate schemes for males and females and prior BP use) to receive either TPTD 20 mcg or identically appearing placebo. Only the statistician will be aware of subject assignment and the pharmacist will distribute the appropriate TPTD or placebo medication. Subjects will be taught by the research nurse the method of daily self-administered subcutaneous injection techniques using TPTD or placebo pens, and provided written instructions for drug administration with a diary to track injections. We have extensive experience teaching subjects to administer TPTD with >90% compliance in elderly populations and subjects in the modelling recruitment phase were willing to take TPTD. Treatment will continue for the 3 months of the proposed study. Even if the fracture heals sooner, these subjects all have osteoporosis and should maintain their osteoporosis treatment for the duration of the double blind trial while other outcomes are evaluated (0 to 3 months).

**Retention:** Subjects will be called weekly during the 3 month blinded trial to monitor side effects and adverse events, and to ensure compliance with the protocol, including medication adherence.

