Randomization will be by gender and bisphosphonate (BP) use creating 4 randomly permuted block randomization lists. We will not exclude prior BP use, however, since the recent use of BP may impact TPTD effect, BP use will be used to create the following strata for randomization within males and females: (1) Recent BP use (greater than one year use within 2 years)/female or (2) Recent BP use (greater than one year use within 2 years)/male (3) distant or never ( $\geq 3$  years since last BP or never users)/female (4) distant or never ( $\geq 3$  years since last BP or never users)/male. We hypothesize that acceleration of pelvic fracture healing by TPTD will not be significantly affected by prior BP use because this skeletal site is largely cancellous bone and we believe that TPTD response is less affected by prior BP use in primarily cancellous sites (vs cortical sites). In addition, initial fracture healing is dependent on callus formation which is not diminished by BP. Furthermore, there was no significant difference in delayed union of the fractured bone between placebo and zoledronic acid after hip fracture. However, given the potential for recent BP use to alter BMD and turnover response to TPTD, we will stratify by BP use to ensure that any effect of BP on TPTD is equally distributed between the placebo and TPTD groups. In addition, we will record length and type of bisphosphonate use as a potential covariate in the analysis to evaluate effect modification by prior BP use.

**Open Label Extension:** After 3 months of placebo versus TPTD, when the data for the primary analysis of all aims has been collected, all persons will be offered to continue TPTD (open label) for 9 months while pain and physical performance are assessed and surveys completed every 3 months. The open label protocol will allow

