## **5. Safety:**

Total serum calcium will be assessed at baseline for study eligibility and then at every visit via standard automated chemistry. Avoiding excessive calcium supplements will help prevent hypercalcemia, therefore we will assess diet and use supplementation only to obtain a total intake of 1000 mg daily. Serum calcium will be reviewed by our safety officer ([name] at HSS). A preplanned algorithm for hypercalcemia (defined as >10.1 mg/dl, the upper limit for our laboratory) requires stopping calcium supplements or reducing dietary intake and repeating the measurement within 2 weeks. If hypercalcemia persists, TPTD/placebo will be withheld. At each monthly visit and during the weekly phone calls while on TPTD/Placebo, adverse events (AEs) or serious adverse events (SAEs), comorbidities and concomitant medication use will be recorded by the nurse and reviewed with the site MD (RN and MD are blinded to treatment). Follow-up for any SAE will occur until it is resolved. All SAEs will be reported to the internal safety officer ([name]) and to the DSMB safety officer and NIAMS (through KAI) within 48 hours of the investigator becoming aware of the SAE. The IRB and FDA (IND 126129; [name]) will be notified of SAEs as per their guidelines. The radiographic evaluations will expose subjects to radiation, however this will not exceed normal clinical care and in fact we worked to reduce exposure using our protocol for focus CT imaging. [name] will serve as the internal safety officer for this study and will review all AE, SAEs and serum calcium for safety. In addition, there is a 3 person DSMB for this study that was appointed by NIAMS. The DSMB will receive reports from the study team every six months for additional safety review. Annual reports will also be filed with the FDA, IRB and NIH.

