**Table 2: Schedule of Procedures**

Procedure	SCR	D1	4 wk	8 wk	12 wk	6 mo	9 mo	12 mo
MMSE, Informed consent	X							
Medical history, medication list and other lifestyle	X							
Physical examination, including height and weight	X							
Screening labs (25(OH)D, PTH, Cr, Ca, prior alkaline phosphatase)	X							
Pelvic radiographs (^until healing occurs-standard care)	X		X^	X^	X^			
Pelvic limited focus CT scan (* as indicated based on cortical bridging and until healing occurs)	X full		X*	X*	X*			
Bone turnover		X	X	X	X			

Calcium for safety		X	X	X	X	X	X	X
Loading dose vitamin D (50,000 IU)	X							
Calcium (total intake 1000 mg) /1000 IU vitamin D		X	X	X	X	X	X	X
Dispense TPTD 20 mcg/day or placebo (blinded for 3 months, then open label TPTD)		X	X	X	X	X	X	X
Adverse event and concomitant medications		X	X	X	X	X	X	X
Numeric Rating scale (NRS) for pain and narcotic use survey and pill count		X	X	X	X	X	X	X
Lower extremity physical function (CSPPS and TUG)		X	X	X	X	X	X	X
Self-reported questionnaires (ADL and SF-36)		X	X	X	X	X	X	X
Telephone calls will occur weekly			X	X	X			

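### Section 6 promises weekly calls during TPTD treatment, but Retention and Table 2 end them at week 12, just as placebo patients may start open-label TPTD

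*Combined protocol and SAP*

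**What the plan says.** Four places in the combined protocol and SAP deal with the calls.

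- Section 6, Teriparatide paragraph: "subjects will be called weekly by the Research Nurse during TPTD treatment". The stated purpose is to detect side effects and trouble with injections. The same paragraph says that when side effects are significant, "volunteers will be told to reduce TPTD administration to every other day until the symptoms abate". It gives no date on which calls end.
- Section 4, Retention: "Subjects will be called weekly during the 3 month blinded trial to monitor side effects and adverse events".
- Section 5: adverse events are recorded at the monthly visits and "during the weekly phone calls while on TPTD/Placebo".
- Table 2: the row "Telephone calls will occur weekly" is marked under weeks 4, 8 and 12 only. The row "Adverse event and concomitant medications" is marked from day 1 through week 12, then at months 6, 9 and 12.

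Under Open Label Extension in Section 4, after the three blinded months "all persons will be offered to continue TPTD (open label) for 9 months", with assessments every three months.

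On calcium, the Monitoring of Hypercalcemia paragraph in Section 6 places the first check four weeks after TPTD is started, when levels peak. It also sets open-label checks at three-month intervals.

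**The concern.** For a patient randomized to placebo, the week-12 switch is the first exposure to TPTD. That is the period for which Section 6 describes weekly calls, yet two of the places that govern site practice end the calls at that point. A site working from Retention and Table 2 would give these new starters much less early monitoring than the original TPTD arm received.

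What is at stake is the timeliness of safety information in the extension. Without scheduled calls, the rule to drop to alternate-day dosing works only if the patient raises the problem unprompted. Non-serious side effects in the first weeks would be recorded late and by recall. The calls also check adherence, so early stopping might not be seen until month 6.

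**Working it through.** The plan states no figure for this point, so the check sets the schedule against the text and then counts.

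**Reading Table 2.** The telephone row has no mark under day 1. Each mark must therefore cover the weeks leading up to that visit; otherwise weeks 0 to 4 would have no calls, contrary to Retention. So the week-12 mark does not stand for calls after week 12. The table has no column between week 12 and month 6.

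**Length of the gap.** Six months is about 26 weeks, and 26 − 12 = 14 weeks. If week 12 is treated as month 3, the gap is three months, about 13 weeks. Scheduled adverse-event contacts inside it, per Table 2: 0 visits and 0 calls. Over their first 12 weeks on drug, patients first randomized to TPTD have 12 weekly calls and 3 follow-up visits.

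**Two readings of Section 6.**

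| Reading of TPTD treatment in Section 6 | Consequence |
|---|---|
| Includes open-label drug | Section 6 requires calls in the extension; Retention and Table 2 leave them out. The defect is a conflict. |
| Blinded study drug only | Section 6 agrees with Retention and Table 2. No calls are planned for new starters. The defect is a gap. |

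Section 5 ties the calls to TPTD/placebo. This leans towards the second reading but does not settle it.

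**Patients affected.** 100 randomized 1:1 gives 50 on placebo. With the planned 20% drop-out, assumed equal across arms, 50 × 0.8 = 40 reach the switch. Acceptance of open-label TPTD is not given, so the range is 0 to about 50.

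**Load of a lighter schedule.** Calls weekly for four weeks and then monthly would fall at study weeks 13, 14, 15, 16, 20 and 24, which is 6 calls. The longest interval without contact becomes 20 − 16 = 4 weeks, and the month-6 visit follows about 26 − 24 = 2 weeks after the last call.

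- Maximum in total: 100 × 6 = 600. If 80 reach week 12 and all accept: 80 × 6 = 480.
- Blinded-phase calls already planned: 80 × 12 = 960 to 100 × 12 = 1,200. At full acceptance the addition is 6/12 = 50% of that.
- In a year with 30 recruits: 30 × 6 / 52 ≈ 3.5 calls a week across all sites, at most.
- Section 6 applied literally to all nine open-label months would mean about 39 calls per participant.

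**Calcium.** Four weeks after a week-12 start is week 12 + 4 = 16. Table 2 has no calcium entry then; the next is month 6. The two rules in the hypercalcemia paragraph therefore give different answers for patients who switch.

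**The case against.** The best defence is that Section 6, read literally, already requires the calls, so a site that reads the whole protocol has no gap. This stands to the extent that the 13 to 14 weeks must be stated as conditional on following Retention and Table 2. It does not remove the defect, because the instructions then disagree and a site may reasonably work from the schedule table.

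The second defence is that quarterly contact in the extension is a deliberate choice. TPTD is marketed for osteoporosis, these patients qualify for treatment, higher-risk patients are excluded, serious events are reported within 48 hours of the investigator becoming aware, and the DSMB receives reports every six months. Patients can also report nausea or dizziness unprompted. All of this lowers the stakes. It does not explain why Section 6 names weekly calls as the means of monitoring TPTD side effects while those starting TPTD at week 12 are scheduled for none. Continued radiographs do not fill the gap: they are for unhealed patients only, their timing is not given, and they are not described as adverse-event contact.

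The third is that weekly calls to everyone for another 12 weeks would be excessive. That is fair: at 50% to 100% acceptance (an assumption) they would add 50% to 100% to the blinded-phase call load. A lighter schedule is enough.

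A reader might infer that the protocol as a whole gives new starters no safety contact, or that every switcher is first asked about side effects at month 6. The documents support neither, because Section 6 can be read to require the calls.

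**Conclusion.** The point holds in conditional form. If sites follow Retention and Table 2, former placebo patients who accept open-label TPTD have no scheduled adverse-event contact for about 13 to 14 weeks after their first dose. If Section 6 covers open-label drug, the fault is a conflict between it and those two places. Either way the text needs an edit.

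This assumes that open-label TPTD starts at or just after the week-12 visit. The number affected lies between 0 and about 50, and the documents give no basis for a higher lower bound.

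It would be wrong to infer that the trial's result is at risk. The gap begins after the blinded phase, so the blinded comparison and the primary outcome are unaffected. Nor do the documents show that events would be lost: month 6 still captures them, later and by recall, and serious-event reporting continues. This is a worthwhile safety correction at modest cost.

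**What to change.** Amend Retention, the Teriparatide paragraph of Section 6 and the telephone row of Table 2 so that they agree. State that nurse adverse-event calls continue early in the extension for all participants who accept TPTD, for example weekly for the first 4 weeks and then monthly to month 6, and state in Section 6 when calls end.

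The calls should go to both original arms. Section 4 says "Only the statistician will be aware of subject assignment", and no unblinding at month 3 is described. The research nurse administers the functional tests and surveys again at 6, 9 and 12 months, and these feed the planned group-by-time analysis. Calling only former placebo patients would reveal their allocation to that nurse.

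For calcium, the sponsor should say whether the four-week rule or the three-monthly rule governs patients who switch. If it is the four-week rule, add a week-16 entry to Table 2.

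The cost is a few sentences, the Table 2 edits and modest nurse time: about 6 short calls per accepting participant, at most about 600 in total. A week-16 calcium check, if adopted for all who accept, would add at most 100 samples (100 × 1).

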## 7. Protocol Details:

**Case-Report Forms:** Case report forms will be used to record screening information, medical history, medication list and lifestyle information (including calcium intake) and the physical exam. The nurses will complete forms for AEs, SAEs and concomitant medications. All AEs and SAEs will be reviewed with the study MD at each site. Standardized forms will also be used for the outcomes: radiologic evaluation of fracture healing, NRS for pain and narcotic use, lower extremity physical function.

**Table 2: Schedule of Procedures**

Procedure	SCR	D1	4 wk	8 wk	12 wk	6 mo	9 mo	12 mo
MMSE, Informed consent	X							
Medical history, medication list and other lifestyle	X							
Physical examination, including height and weight	X							
Screening labs (25(OH)D, PTH, Cr, Ca, prior alkaline phosphatase)	X							
Pelvic radiographs (^until healing occurs-standard care)	X		X^	X^	X^			
Pelvic limited focus CT scan (* as indicated based on cortical bridging and until healing occurs)	X full		X*	X*	X*			
Bone turnover		X	X	X	X			

Calcium for safety		X	X	X	X	X	X	X
Loading dose vitamin D (50,000 IU)	X							
Calcium (total intake 1000 mg) /1000 IU vitamin D		X	X	X	X	X	X	X
Dispense TPTD 20 mcg/day or placebo (blinded for 3 months, then open label TPTD)		X	X	X	X	X	X	X
Adverse event and concomitant medications		X	X	X	X	X	X	X
Numeric Rating scale (NRS) for pain and narcotic use survey and pill count		X	X	X	X	X	X	X
Lower extremity physical function (CSPPS and TUG)		X	X	X	X	X	X	X
Self-reported questionnaires (ADL and SF-36)		X	X	X	X	X	X	X
Telephone calls will occur weekly			X	X	X			

### Specific Methodology:

**CT imaging:** The first CT image that identifies the fracture will be a standard pelvic CT. For follow-up CT imaging, we will utilize a novel method to assess fracture healing (Focus CT). Presently, plain radiographs and serial computed tomography are completed every month, with a radiation dose of 7.5 mSv per exam. Focus CT, which will reduce radiation exposure, could be used in place of standard serial CT to assess the healing process. A low dose technique using an automatic tube current modulation (ATCM) technique was developed for the pelvis, making it possible to achieve a reduction in radiation dose to the patient. It is important to reduce medical radiation exposure as much as possible, the "as low as reasonably achievable" (ALARA) concept, which could be achieved by utilizing Focus CT scanning to the area of specific interest e.g. limiting radiation exposure to the fracture site alone. Focus CT is accomplished by decisions regarding the collimation, pitch, tube voltage, current, and rotation and by reducing the scan field of view. Scanning a smaller Field of View (FOV) alone resulted in an estimated reduction of radiation exposure of between 40-68% relative to a standard full FOV CT of the pelvis. Additionally, there was no difference in the diagnostic quality of the Focus CT relative to the baseline full FOV CT for tracking fracture healing, with both musculoskeletal radiologists noting a 100% intra-observer concordance in their findings between the full FOV and Focus CT images for each case.

**Initial CT Scan:** After obtaining frontal and lateral topograms of the pelvis (120 kV; 10 mA), helical CT of the pelvis will be obtained from the L5 vertebral body through the ischia without intravenous contrast (GE Light Speed Pro 32 CT). Scans at both sites will be obtained following the same protocol with slice thickness of 2.5 mm, interval of 1.25 mm, keV of 120, and Auto mA with range of 100-500 and noise index of 15.17. Sagittal and coronal reformats will also be created and reviewed. The initial CT scan will define all pelvic fractures including pubic rami and sacrum. The fracture will be classified as: single or multiple rami fractures; presence of sacral fracture and amount of displacement with 3 categories: Minimal/No displacement, Mild displacement, Moderate displacement.

**Focus CT Scan (Follow-up):** After obtaining frontal and lateral topograms of the pelvis (120 kV; 10 mA), focused helical CT will be obtained from 1 cm above the superior pubic ramus to 1 cm below the inferior ischiopubic ramus without intravenous contrast (GE LightSpeed VCT). Scans will be obtained with a slice thickness of 2.5 mm with interval of 1.25 mm, keV of 120, and Auto mA with range of 100-500 and noise index of 15.17. Sagittal and coronal reformats will also be created and reviewed. The focus CT will only evaluate superior and inferior pubic fractures, since CT determination of sacral fracture healing is difficult. At any visit where some cortical bridging is noted on the x-rays, a CT is performed and cortical bridging will be quantified with bridging of 3 or 4 cortices as "healing", 1 or 2 cortices with "partial healing", and 0 cortices with "minimal/no healing". If there are multifocal fractures, cortical bridging at each site will be evaluated and an average of cortical bridging score (0 to 4) will be recorded. If full union is noted by focus CT (evaluated by both radiologists), then no further radiographs or CT scans are needed, although all other assessments will continue. At 3 months the remaining patients who still haven't healed will undergo a focused limited low dose CT to quantify the degree of cortical bridging after 3 months of treatment. Radiographs and CT scans will continue during the open extension in those who have not yet healed. CT scans will be evaluated independently by [name], who will be blinded to treatment group. If there is a discrepancy between the score for cortical bridging (1 score difference in the reading) between them, a third reader as part

of the Contract Imaging Coordinating Center role at Weill Cornell Radiology will be brought in to blindly adjudicate the discrepancy. All CT images will be de-identified and archived using IDEAL (Imaging Data Evaluation and Analytics Lab) that houses the research PACS system with individual data devoid of any PHI and only having a subject ID.

The research nurse will record the pain assessment, administer physical performance tests using standard methodology and administer all surveys as detailed below. **Pain assessment:** The research nurse will administer the NRS for pain. Using a scale from 0 (no pain) to 10 (worst pain imaginable), the subject will report how intense their pain is now and how intense it was on average last week. They will also report how much relief from pain they have achieved using treatment for pain. For this they will use a scale of 0% (no relief) to 100% (complete relief). They will also be asked about all of the pain medications they are currently taking. In addition, the nurse will ask the subject to bring any pain medications being used to each visit so that a pill count of use can be made. **Physical Performance Measures**: The **walk** is a timed walk at normal walking speed with a meter run-in before starting the timed portion and another meter at the end of the course in order to measure each subject walking at normal speed over 4 meters. Devices such as canes and walkers are allowed and their use will be recorded. The research nurse will record the use of aids and the time required to walk on the case report form. A straight backed chair will be placed against a wall and subjects will be asked to stand with their arms folded across their chest. If they can perform this task they will be asked to repeat it five times. The research nurse will record the amount of time for 5 **chair stands** to be completed on the case report form. The **balance test** measures the ability of subjects to maintain balance for 10 seconds in each of 3 positions: side-by-side, semi-tandem, and tandem foot positions. The test will be stopped if the subject cannot maintain any position for 10 seconds. The final measure for balance is the sum of the time from the three positions (range 0-30 seconds). Subjects unable to perform any of the above three tests will be assigned a 0 score. During the course of the balance test there will be two trained individuals standing in an appropriate manner to protect a patient against any falls. The research nurse will complete the case report form and follow written instructions in the detailed clinical protocol. Scores will be calculated for the CSPPS based on these tests. **Timed Up and Go Test (TUG)**: Patients will be asked to wear their regular footwear and told that they can use a walking aid if needed (this will be recorded). The test begins by having the subject Stand up from the chair, walk to the line on the floor at a normal pace, turn, walk back to the chair at a normal pace and Sit down again. The person administering the test will time the subject using a stopwatch and record the time on case report forms.

**Surveys:** All performance tests and surveys will be administered by the research nurse, who is blinded to treatment status during the study visit. Study participants will complete several questionnaires, including assessments of ability to perform activities of daily living (ADLs) and the physical component of SF-36. The Barthel activity of daily living (ADL) survey is a patient self-reporting survey to assess mobility and self-care. Subjects are asked a series of questions and asked to respond with a multiple choice answer about difficulty the level of difficulty with which they are able to complete each task, the baseline ADL will evaluate pre-fracture and current ADLs. For the assessments of ADLs, subjects will report 1 of 3 responses, similar to those used in WHAS: 1) no difficulty, 2) little of some difficulty, 3) a lot of difficulty or unable to do without help from a person or special equipment. For the SF-36, only the physical sub-scales will be used: Physical Function (PF), Role-Physical (RP), Bodily Pain (BP), and General Health (GH). Subjects will be asked questions about general health and physical limitations over the previous 4 weeks (before the fracture during screening and then since the fracture will be asked at baseline). All responses are recorded CRF and scored.

**Biochemistry:** After blood samples are obtained, all processing and aliquoting procedures are performed in the Biochemistry Unit of the Regional Bone Center of Helen Hayes Hospital. Biochemical evaluations will include those used for exclusion criteria, efficacy (bone turnover) and safety (serum calcium). All efforts are made to prepare aliquots according to the assays planned to avoid repeated thawing and refreezing. For this project, serum samples for bone turnover (PINP and CTX) and serum 25(OH)D will be stored in separate 1 ml aliquots in a -80 degree freezer. All biochemical efficacy assays from an individual patient will be performed in the same assay to avoid inter-assay variability in individual patients. All assays planned in this proposal have been performed for a number of years in the RBC Laboratory. Specific methods and quality control data for each assay have been previously reported.

**Data Management:** Subjects will be enrolled at each Hospital with each site having a dedicated research coordinator. All identifying information will be kept on one form in a locked file cabinet at each site along with the consent form. A study ID number will be given to each person and completed CRF's will be sent to the

data manager on paper. We will enter these into a Microsoft Access database with built-in logical checks. Site monitoring of the type that is done for multi-site pharmaceutical studies will be completed. Data collection forms have been centrally designed and will be distributed. A case report book for each subject will be prepared to contain each case report form required to be completed according to the protocol. Each case report form has standard header information identifying the study subject by research identifier, when the data is collected, the location where data is collected and a unique identifier signifying the identity of the research staff member responsible for the validity of the data recorded on the form. Forms recording the results of clinical and/or laboratory evaluations will have countersignature by a study physician to attest to the medical review of the data for safety. Data that is de-identified will be entered into the database. While field ranges and valid value codes will be checked in the data entry screen application, central data monitoring programs will monthly summarize data quality: a) recruitment, enrollment and retention; b) visit attendance and missed visits; c) missing forms; d) within form edit checks on item ranges and valid values, skip jumps, and across-item logical consistency checks; e) between form within visit logical consistency checks; f) within form between visit logical consistency checks. A routine suite of reports summarizing the results of the above data quality reviews will be sent back to the research study coordinator at each site and progress at correction or documentation of suspicious values will be monitored through edit review and the next month's reports. The PI and Co-PI will be kept apprised of data quality and targets for data timeliness, accuracy and documentation quality will be presented and periodically reviewed with research staff. Error checking programs written in SAS, will be run periodically. All data will be imported into SAS for analysis. The database and randomization list will be password protected, and backed up daily.

**Statistical Plan:** There will be no interim analysis and missing outcome data will not be imputed. Statistical analysis will be performed using SAS software (Cary NC). Between group differences at baseline will be compared with t-tests or Wilcoxon rank sum tests and chi-square tests as appropriate (p-value <0.05 for significance). Randomization by the method of randomly permuted blocks will be created for gender and BP use groups. Our primary analysis is ITT analysis and our primary outcome (SA#1) is the categorization of the level of bridging seen on focus CT into the scores from 0 to 4, described above between 0 and 3 months. The difference in cortical bridging will be evaluated by a 2x5 chi-square (group x score) with a trend test (Jonckheere-Terpstra) to see whether TPTD treated "trend" to have more higher bridging scores than the placebo group. We expect 30% - 50% superiority with TPTD at 3 months. This categorical outcome will be further analyzed with generalized estimating equations (GEE) for longitudinal repeated measures assuming a Poisson distribution with weighting from logistic regression analysis of the missingness pattern. Secondary analyses of covariates, sensitivity analyses and the "per protocol" analysis will incorporate the aforementioned approach into this aim's GEE analysis. This analysis addresses the question "Do patients treated with TPTD show more rapid fracture healing than those given placebo? For SA #2, we anticipate that the difference in pain score between the TPTD and placebo groups in the proposed study will be > 30% at each monthly time point (0-3 months). We will use a between-groups linear mixed model for repeated measures (LMMrm) to estimate the primary outcome of the difference in the mean within-subject change from baseline in the two groups at the end of the placebo controlled trial (0-3 months) and again to explore change from 3 to 12 months in the open label extension. In addition, narcotic and non-narcotic pain medication use will enter the model as time-dependent covariates. This analysis addresses the two questions, "Do patients treated with TPTD show more rapid reduction in reported pain level than those not so treated? If so, when?" For SA#3, the CSPPS is the outcome. A linear mixed model for repeated measures (LMMrm) will be used with fixed effects of treatment group (TPTD vs. placebo), time (D1, 4-, 8- and 12-wk) and their interaction, the baseline level of the CSPPS and days from injury to randomization entered as covariates, and a within-subject covariance structure selected by empirical methods prior to hypothesis testing. This plan will be repeated for the "per protocol" analysis in which subjects are limited to those showing 80% or greater compliance over the 12-week trial. This statistical plan addresses the two clinical questions, "Do patients treated with TPTD recover lower limb function faster than those not so treated? If so, when?" LMMrm will be used to analyze data from 3-12 months and assess group by time interaction. We will group on prior BP exposure strata to account for possible heterogeneity in the R-side covariance structure.

Imbalances in group characteristics at baseline (p-values < 0.20) will be assessed as covariates in secondary analyses and findings of significant effect modification will be followed-up with sensitivity analyses. Cumulative

exposure to treatment will be entered as time dependent random effect to incorporate compliance and non-completer data. Other outcomes will be similarly analyzed in secondary analyses. The following variables will be considered and tested as potential covariates in these models using  $p<0.2$  correlation with outcome as criterion: gender, age, baseline 25(OH)D, pre-fracture SF36 physical function score, Charlson Comorbidity scale, concomitant medications, recent BP use, fracture severity (displacement) and fracture category (single or multiple fractures or sacral and pubic).

**Sample Size Justification:** We will recruit 100 female and male subjects over 4 years (30, 30, 30, 10) to yield 80 analyzable subjects completing 3 months of treatment after assuming a 20% overall drop-out rate. Power and sample size were calculated for SA#1 fracture healing by radiographic studies: if 100% of TPTD and 60% of placebo have completed fracture healing by three months, 40 subjects per group provides  $> 95\%$  power with 1% alpha to detect this difference based on an analysis of proportions. For the Timed Up and Go Test assuming Peichel's results (at week 12 TPTD =  $22.9 \pm 7.7$  vs Placebo =  $54.3 \pm 19.9$ ), a SD of 18 and a week 4 to 12 pattern of rapid fracture healing in the TPTD group (at week 8 100% vs 9% in Placebo). A repeated measures ANOVA with a Hotelling-Lawly F-test, the same as the Wald test in the LMMrm model with unstructured covariance matrix, shows 90% power at 1% alpha is achieved for the fixed treatment effect with 33 subjects per group and time-by-treatment interaction with 36 subjects per group (SAS 9.4 GLMPOWER).
